6.2. Toxicity Analysis

6.2.1. Nephrotoxicity: Nephrotoxicity will be assessed using the KDIGO criteria to define AKI. The nephrotoxicity endpoint will be met if subjects meet criteria for any stage of AKI by the KDIGO criteria using measured serum creatinine (Table 2). The degree of AKI will also be described by KDIGO stage. Time to renal recovery after cessation of PMB and the proportion of patients with renal recovery by hospital discharge will also be assessed. Renal recovery is defined as resolution of all KDIGO criteria for AKI.

Table 2: Definition of AKI using the KDIGO criteria

Stage	Serum Creatinine
1	1.5 – 1.9 x baseline OR ≥ 0.3 mg/dL increase from baseline
2	2.0 – 2.9 x baseline
3	≥ 3.0 x baseline OR

	$\geq 4 \text{ mg/dL}$ OR Initiation of renal replacement therapy
--	--

6.2.2. Neurotoxicity: Neurotoxicities will be assessed by patient self-report. The type of toxicity, anatomic site of toxicity, and severity will be assessed by the study personnel using the National Cancer Institute: Common Terminology Criteria for Adverse Events (NCI:CTCAE) scale.²⁵

Table 3: NCI:CTCAE terminology and definitions for potential neurotoxicities

CTCAE Term	Definition
Apnea	A disorder characterized by cessation of breathing
Ataxia	A disorder characterized by lack of coordination of muscle movements resulting in the impairment or inability to perform voluntary activities
Confusion	A disorder characterized by a lack of clear and orderly thought and behavior
Dizziness	A disorder characterized by a disturbing sensation of lightheadedness, unsteadiness, giddiness, spinning, or rocking
Dyspnea	A disorder characterized by an uncomfortable sensation of difficulty breathing
Hallucinations	A disorder characterized by a false sensory perception in the absence of an external stimulus
Hearing impairment	A disorder characterized by partial or complete loss of the ability to detect or understand sounds resulting from damage to ear structures
Muscle Weakness	A disorder characterized by a reduction in the strength of muscles in multiple anatomic sites
Paresthesia	A disorder characterized by functional disturbances of sensory neurons resulting in abnormal cutaneous sensations of tingling, numbness, pressure, cold, and/or warmth
Peripheral motor neuropathy	A disorder characterized by damage or dysfunction of peripheral motor nerves
Peripheral sensory neuropathy	A disorder characterized by damage or dysfunction of peripheral sensory nerves
Psychosis	A disorder characterized by personality change, impaired functioning, and loss of touch with reality.
Respiratory Failure	A disorder characterized by impaired gas exchange by the respiratory system resulting in hypoxia and a decrease in oxygenation of the tissues that may be associated with an increase in arterial levels of carbon dioxide
Seizure	A disorder characterized by sudden, involuntary skeletal muscle contractions of cerebral or brain stem origin

Table 4: NCI:CTCAE terminology and grade for potential neurotoxicities

CTCAE Term	Grade 1	Grade 2	Grade 3	Grade 4	Grade 5
Apnea	-	-	Present; medical	Life-threatening respiratory or	Death

			intervention indicated	hemodynamic compromise; intubation or urgent intervention indicated	
Ataxia	Asymptomatic; clinical or diagnostic observations only	Moderate symptoms; limiting instrumental ADL	Severe symptoms, limiting self-care ADL; mechanical assistance indicated	-	-
Confusion	Mild disorientation	Moderate disorientation; limiting instrumental ADL	Severe disorientation; limiting self-care ADL	Life-threatening consequences; urgent intervention indicated	-
Dizziness	Mild unsteadiness or sensation of movement	Moderate unsteadiness or sensation of movement; limiting instrumental ADL	Severe unsteadiness or sensation of movement; limiting self-care ADL	-	-
Dyspnea	Shortness of breath with moderate exertion	Shortness of breath with minimal exertion; limiting instrumental ADL	Shortness of breath at rest; limiting self-care ADL	Life-threatening consequences; urgent intervention indicated	Death
Hallucinations	Mild hallucinations (e.g. perceptual distortions)	Moderate hallucinations	Severe hallucinations; hospitalization not indicated	Life-threatening consequences; threats of harm to self or others; hospitalization indicated	Death
Hearing Impairment	Subjective change in hearing in the absence of documented hearing loss	Hearing loss with hearing aid or intervention not indicated; limiting instrumental ADL	Hearing loss with hearing aid or intervention indicated; limiting self-care ADL	Decrease in hearing to profound bilateral loss; nonservicable hearing	-
Muscle weakness	Symptomatic; perceived by patient but not evident on physical exam	Symptomatic; evident on physical exam; limiting instrumental ADL	Limiting self-care ADL	-	-
Paresthesia	Mild symptoms	Moderate symptoms; limiting instrumental ADL	Severe symptoms, limiting self-care ADL	-	-
Peripheral motor neuropathy	Asymptomatic; clinical or diagnostic	Moderate symptoms; limiting	Severe symptoms, limiting self-care ADL	Life-threatening consequences; urgent	Death

	observations only	instrumental ADL		intervention indicated	
Peripheral sensory neuropathy	Asymptomatic	Moderate symptoms; limiting instrumental ADL	Severe symptoms, limiting self-care ADL	Life-threatening consequences; urgent intervention indicated	-
Psychosis	Mild psychotic symptoms	Moderate psychotic symptoms (e.g. disorganized speech; impaired reality testing)	Severe psychotic symptoms (e.g. paranoid, extreme disorganization); hospitalization not indicated, new onset	Life-threatening consequences, threats of harm to self or others; hospitalization indicated	Death
Respiratory Failure	-	-	-	Life-threatening consequences; urgent intervention, intubation, or ventilator support indicated	Death
Seizure	Brief partial seizure and no loss of consciousness	Brief generalized seizure	New onset seizures (partial or generalized); multiple seizures despite medical intervention	Life-threatening consequences; prolonged repetitive seizures	Death

Abbreviations: ADL, activities of daily living

*Instrumental ADL refer to preparing meals, shopping for groceries or clothes, using the telephone, managing money, etc.

**Self-care ADL refer to bathing, dressing and undressing, feeding self, using the toilet, taking medications, and not bedridden

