We propose to measure the plasma concentrations of PMB in adult patients with CF receiving intravenous therapy as a part of their routine care and to use these measured concentrations to build population pharmacokinetic models. The population pharmacokinetic modeling approach will allow the assessment of the impact of patient specific covariates (i.e. weight, renal function) on pharmacokinetic parameters. Patients will be monitored for nephrotoxicity and neurotoxicity to ensure that PMB has an acceptable

margin of safety in this patient population. This investigation will be the first to prospectively assess the pharmacokinetics and toxicities of PMB in this patient population and will facilitate optimal use of this compound in the management of acute pulmonary exacerbations of CF.

4. Specific Aim/Hypothesis

4.1. Measure the plasma concentration of PMB in adult CF patients receiving intravenous therapy. Adult patients with CF often receive multiple courses of antipseudomonal antibiotics over the course of their disease resulting in the evolution of multi-drug resistant (MDR) *P. aeruginosa* pulmonary colonizers. The polymyxins, colistin and PMB, frequently retain activity against MDR gram-negative bacteria. Colistin has historically been the most commonly used polymyxin in patients with CF; however, new pharmacokinetic (PK) and toxicity data obtained from non-CF populations suggest that PMB may achieve more consistent exposure with lower associated toxicity. We aim to measure concentrations of PMB in plasma samples obtained from adult CF patients treated with polymyxin B using liquid chromatography–tandem mass spectrometry (LC-MS/MS).

4.2. Characterize the pharmacokinetics of PMB in adult CF patients. There are three major population PK studies which inform the dosing of PMB and one small study including patients with CF. These studies suggest that the clearance of PMB is not related to patient body weight and have discordant results regarding patient renal function. Therefore, underweight patient populations with excellent renal function, such as CF, may be at risk for underdosing with traditional weight-based regimens. We aim to use population pharmacokinetic modeling to characterize the PK of fixed-dose PMB in this special population and assess the effect of patient-specific covariates (e.g., body weight, renal function) on PK parameters.

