4.3. Determine the safety of PMB therapy in adult CF patients. Polymyxin use is limited to salvage therapy for MDR gram-negative bacterial infections and cases of allergy, intolerance, or adverse effects to alternative agents due to the significant toxicities related to these compounds. Nephrotoxicity is the most common dose-limiting toxicity; however, it has been poorly characterized with PMB in patients with CF. Neurotoxicity has also been reported and occurs with moderate frequency with colistin in studies of patients with CF. We aim to characterize PMB-associated nephrotoxicity using the Kidney Disease: Improving Global Outcomes (KDIGO) criteria and neurotoxicity via patient self-report.

5. Study Methodology

5.1. Study design: Single-center, open-label, non-interventional, pharmacokinetic study.

5.2. Inclusion criteria: Study subjects will be identified by investigators in the course of providing clinical care or by means of reports built in TheraDoc® Clinical Surveillance software (version 4.4; Premier Inc, Salt Lake City, UT) or built directly into the electronic medical record (EPIC Systems, Madison, WI). Subjects fulfilling the following criteria will be eligible for inclusion:

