5.3.2. Pregnancy

5.3.3. Unable to provide informed consent

5.4. Study Timeline

[figure not shown]

Figure 1: Study Timeline and Procedures. Abbreviations: CF, cystic fibrosis; LC-MS/MS, liquid chromatography tandem mass spectrometry, Scr, serum creatinine

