5.6. Dosing and Administration

5.6.1. The dose and duration of infusion for PMB will be determined at the discretion of the prescribing physician in the course of routine clinical care. There is no study intervention on the dosing and administration of PMB.

5.6.2. The recommended dosing schedule for intravenous polymyxin B at Michigan Medicine consists of an initial weight-based loading dose (2 mg/kg, maximum of 200 mg) followed by 100 mg every 12 hours for the duration of therapy as determined by the clinician. A reduction of the maintenance dose to 75 mg every 12 hours is recommended for patients with total body weight less than or equal to 50 kg.

5.7. Sampling:

5.7.1. Blood samples will be collected from enrolled patients at 5 time points during a single dosing interval under steady-state conditions. Sampling will occur on any day of therapy immediately prior to and following a single dose of PMB. The infusion time is selected at the discretion of the prescribing physician; thus the sampling schema is described based on the duration of infusion (Table 1).

Table 1: Sample collection times

Sample Code	Collection Timepoint	Collection Time Relative to Duration of Infusion (t_{inf})
C_0	Prior to Start of Infusion	0 hour
C_1	End of Infusion	$t_{inf} + 0$ hour
C_2	One Hour after End of Infusion	$t_{inf} + 1$ hour
C_3	Three Hours after End of Infusion	$t_{inf} + 3$ hours
C_4	Eight Hours	8 hours

5.7.2. Blood samples will be collected via one of three sampling methodologies: peripheral venipuncture, peripheral intravenous catheter, or a central venous catheter (e.g., PICC, Port). The method of obtaining blood samples will be determined by study personnel and will consider patient preference, patient safety, and the likelihood of obtaining adequate samples. Insertion of, care for, and sampling from indwelling catheters will be performed per hospital policy.

5.7.3. The procedure for obtaining and processing blood samples can be found in the Laboratory Protocol document in the Appendix (10.1).

5.8. Demographic and Clinical data: Study team members will obtain demographic and clinic data needed to describe the study population and build pharmacokinetic models. Data will be abstracted from DataDirect or obtained directly from the medical record for each index encounter. Data recorded directly from the medical record will be stored in REDcap.

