5.8.1. Demographic: comprehensive demographic data will be obtained from DataDirect. Examples of variables of interest include race and sex.

5.8.2. Encounter: comprehensive encounter data will be obtained from DataDirect. Example variables of interest include age, weight, height, body mass index, admission and discharge dates, and sites of care.

5.8.3. Diagnosis: comprehensive codified diagnosis data will be obtained from DataDirect.

Example diagnoses of interest include comorbid conditions, admission diagnoses, and discharge diagnoses

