5.8.6. Laboratory: comprehensive laboratory information, including microbiology, will be

obtained from DataDirect. Example laboratory values of interest include aminoglycoside or vancomycin drug concentrations, serum creatinine, blood urea nitrogen, sodium, potassium, CO₂, albumin, total bilirubin, white blood cell count, platelet count, hemoglobin, hematocrit, total lymphocyte count, pH, PaO₂, bicarbonate, procalcitonin, erythrocyte sedimentation rate, c-reactive protein, and culture results.

5.8.7. Vitals: comprehensive vital signs and fluid inputs and outputs will be obtained from

DataDirect. Example vitals of interest include mechanical ventilation, fraction of inspired oxygen (FiO₂), oxygen saturation, temperature, blood pressure, heart rate, respiratory rate, urine output, Glasgow Coma Scale score (GCS), dietary information.

5.8.8. Outcome: hospital length of stay, mortality, readmission rate. Results of spirometry, including forced expiratory volume in 1 second (FEV1).

5.9. Assay: Plasma concentrations of polymyxin B, comprising both polymyxin B1 and B2 components, will be determined using LC-MS/MS.

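### Patient self-report is the only source named for neurotoxicity, yet the grading table includes states that self-report cannot or may not find, and no written rule requires an event to be new or worse than before PMB

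*Combined protocol and SAP*

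**What the plan says.** - The aim in 4.3 is to characterize "neurotoxicity via patient self-report". The method in 6.2.2 repeats it: "Neurotoxicities will be assessed by patient self-report".
- Study personnel come in at the next step, using CTCAE: "The type of toxicity, anatomic site of toxicity, and severity will be assessed by the study personnel". They classify; the text does not say that they look for events by another route.
- The Background (section 3) promises that "Patients will be monitored for nephrotoxicity and neurotoxicity", but gives no method.
- Section 5.8 collects chart data for each index encounter. Under 5.8.3, "Example diagnoses of interest include comorbid conditions, admission diagnoses, and discharge diagnoses". Under 5.8.7, "Example vitals of interest include mechanical ventilation, fraction of inspired oxygen", and the same list includes the Glasgow Coma Scale (GCS). Mortality is an outcome field in 5.8.8. Section 6.2.2 refers to none of these.
- Section 6.3.3 reports toxicity rates as counts and percentages, with no grade threshold and no condition of change from before treatment.
- The figure in 5.4, titled "Study Timeline and Procedures", is missing from the available text.

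**The concern.** A safety rate depends on how cases are found and on what counts as a case. Here the finding method and the grading table do not match: the table has rows and grades that depend on observation, on a chart entry or on a death record, while the stated source is what the patient says. Events at the severe end are the ones most exposed to being missed.

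The case definition is also open at the mild end. Patients with chronic, progressive lung disease, often treated during an exacerbation, may be short of breath before the first dose, and the dyspnea grades describe a state rather than a change.

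Safety is one of three aims, and 7.1.1 says the data will be used to ensure safety at commonly used doses. The Background calls polymyxin neurotoxicity poorly characterized, especially for polymyxin B, and cites pediatric colistin rates from 0 to 97.3%. A rate without a firm case definition would do little to narrow that.

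**Working it through.** The plan gives no expected neurotoxicity rate, sample size justification or precision target, so there is no figure of its own to reproduce. The check is a count from Tables 3 and 4 and a comparison of sections.

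**1. Detection: Table 4 against self-report (14 terms).**
- Grade 5 is death for apnea, dyspnea, hallucinations, peripheral motor neuropathy, psychosis, respiratory failure and seizure: 7 of 14. No death can be self-reported.
- No grade below 3 for apnea (starts at Grade 3) and respiratory failure (starts at Grade 4): 2 of 14. Grade 4 of both involves intubation or urgent intervention.
- Grade 1 is asymptomatic for ataxia, peripheral motor neuropathy and peripheral sensory neuropathy: 3 of 14. By definition there is no symptom to report.
- Severe confusion and psychosis may leave a patient unable to give a reliable account. This is clinical inference, not table wording.

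On the table's own wording, the terms with at least one grade beyond self-report are the 7 with death plus ataxia and sensory neuropathy (motor neuropathy is already among the 7): 7 + 2 = 9 of 14. Apnea and respiratory failure are also among the 7.

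**2. Is another source linked?** Section 6.2.1 defines AKI by measured serum creatinine, which is a 5.8.6 field. Section 6.2.2 has no matching link to diagnoses, ventilation, GCS or mortality. The data exist; the rule to use them for this endpoint is not written.

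**3. Baseline.** AKI in Table 2 is defined mainly by change from baseline. For neurotoxicity, Table 4 has change wording for hearing impairment, psychosis (Grade 3) and seizure (Grade 3), which is 3 terms. Table 3 adds muscle weakness and respiratory failure: 3 + 2 = 5 of 14. Dyspnea has none in either table. Its Grades 1, 2 and 3 are breathlessness with moderate exertion, with minimal exertion and at rest, each an absolute state.

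**4. Size.** The only number of subjects is a maximum of 20, in the supply list of 10.1. One patient moves a rate by 1/20 = 5.0 points. With fewer patients it is more: 1/15 = 6.7 and 1/10 = 10.0 points (15 and 10 are assumptions).

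**5. Direction.** Let p be the true rate, s the share of true cases that self-report captures, and d the share of patients whose prior breathlessness is counted. For an overall any-term rate, treating the two as independent, apparent rate = 1 - (1 - p·s)(1 - d). With p = 30% and s = 70% (both assumed), p·s = 21%, and:

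| d (assumed) | Calculation | Apparent rate |
|---|---|---|
| 0% | 1 - 0.79 × 1.0 | 21.0% |
| 10% | 1 - 0.79 × 0.9 | 28.9% |
| 30% | 1 - 0.79 × 0.7 | 44.7% |

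Against a true 30%, the result can be too low, nearly right by accident, or too high. The documents give none of the three inputs.

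**The case against.** The strongest reply is that this is a descriptive analysis in a non-interventional study, with no test or decision threshold, and that much of the needed information is already collected. That stands, and it limits the weight of the point. By-term reporting is also already possible, because type, site and severity are recorded and 6.3.3 defines no composite; a false dyspnea would then change only the dyspnea row. Self-report also suits paresthesia, which the Background names as the most common manifestation.

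Four stronger readings are tempting, and the documents do not support them.

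- *The plan counts baseline breathlessness as toxicity.* It does not say so. The aim speaks of toxicity associated with PMB and the tables of potential neurotoxicities, so some judgement of cause is implied. What is missing is a written rule, so two assessors could code the same patient differently.
- *Chart data are barred from the toxicity analysis because 5.8 describes them as "needed to describe the study population and build pharmacokinetic models".* Creatinine from the same section already feeds 6.2.1, and 5.8.8 is headed as outcome data. That sentence does not confine their use.
- *Most seizures would go unreported.* Nothing in the documents supports a frequency. Seizure belongs here because of its life-threatening and fatal grades.
- *No baseline assessment or questioning schedule exists.* Figure 1 is not available and could contain either, so absence is shown only for the readable text.

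**Conclusion.** The point holds, mainly on detection. Self-report is the only source named in the readable text, and it does not match a table in which 9 of 14 terms have a grade that, on the table's own wording, is fatal or without symptoms. Following the stated method can therefore undercount.

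The baseline gap is real but weaker, because the wording implies a judgement of cause without setting a rule for it.

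The consequence is confined to a descriptive safety rate. A reader might infer a known upward or downward bias, but neither its size nor its net direction can be derived. What can be said is that each misclassified or missed patient is worth 5 percentage points at 20 subjects and more with fewer. This rests on the supply-list maximum of 20 and on Figure 1 containing nothing that settles the matter. The PK analysis is unaffected.

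**What to change.** In 6.2.2:
- Supplement self-report with diagnoses (5.8.3), ventilation and GCS (5.8.7) and mortality (5.8.8) for apnea, respiratory failure, seizure, confusion, psychosis and Grade 5 events. Use mortality to flag deaths for review, since that field alone does not show that a listed term was the cause.
- State that asymptomatic Grade 1 ataxia and neuropathies are not captured by self-report, and do not report them as absent.
- Count a term only if it is new or at least one grade worse than its pre-PMB grade. Take that grade from the index-encounter chart, or from patient recall flagged as such.

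In 6.3.3, report rates by term, and show dyspnea, apnea and respiratory failure separately from any overall rate. They should not be dropped, because the Background names rare respiratory compromise among the manifestations.

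If Figure 1 already sets baseline or assessment times, refer to them in 6.2.2.

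Cost: a little more abstraction from fields already collected, plus recording a pre-PMB grade for each term. Recall error will affect patients enrolled after the first dose, which 5.7.1 makes possible by allowing sampling on any day of therapy. The cause of new respiratory events will remain uncertain, which is why they are shown apart.

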6.3. Statistical Analysis

6.3.1. Baseline demographic and clinical data: Baseline demographic and clinical data will be assessed using descriptive statistics. Variables will be summarized as mean (standard deviation), median (5th, 95th percentile), or number (percentage) as indicated.

6.3.2. Population pharmacokinetic analysis: Model goodness-of-fit of the observed data will be assessed by regression with an observed-predicted plot. Between-subject variability will be quantified using coefficients of determination. Model discrimination will be based on log-likelihood (-2LL) and Akaike's Information Criterion (AIC) objective function values as well as diagnostic plots. Predictive performance evaluation will be based on weighted mean bias and the bias-adjusted weighted mean precision.

6.3.3. Toxicity analysis: Nephrotoxicity and neurotoxicity rates will be summarized as number (percentage). Time to renal recovery will be summarized as mean (standard deviation) or median (interquartile range) days as indicated while renal recovery by hospital discharge will be summarized as number (percentage).

7. Benefits and Risks

7.1. Benefits:

7.1.1. Current CF Foundation guidelines recommend that two antibiotics with activity against *P. aeruginosa* as the standard of care for treatment of acute pulmonary exacerbations. Many adult CF patients have had extensive lifetime exposure to antipseudomonal antibiotic therapy and may require therapy with last line agents due to multi-drug resistance in clinical isolates. The polymyxins, colistin and polymyxin B, are often required as combination salvage therapy for isolates with documented resistance to aminoglycosides or fluoroquinolones. Polymyxin B has significant pharmacokinetic advantages to colistin for CF patients; however, limited data exist in this patient subpopulation to guide dosing in practice. The data generated by this study will be used to confirm dosing of polymyxin B in this population and ensure safety with commonly administered doses extrapolated from non-CF patient populations. There is no direct benefit to patients enrolled in the study at the time of enrollment; however, patients treated with polymyxin B at the time of the study are at risk for re-infection with MDR organisms in the future. Therefore, PK data obtained in this study could inform the dosing of polymyxin B for the treatment of future infections with MDR organisms.

7.1.2. Patients will not experience direct benefit from this study. Patients will not be informed of study results.

